# Open Label Randomized Controlled Trial to Assess the Impact of prophylactic exposure to tenofovir gel on the efficacy of subsequent tenofovir-containing antiretroviral therapy on viral suppression

## ABBREVIATIONS AND ACRONYMS

3TC	Lamivudine
AE	adverse event
AIDS	Acquired Immunodeficiency Syndrome
ABC	Abacavir
ARVs	Antiretrovirals
AZT	Zidovudine
CAPRISA	Centre for the AIDS Programme of Research in South Africa
CAT	CAPRISA AIDS Treatment
CD4	Cluster of differentiation 4
CDC	Communicable Disease Centre
CRF	Case Report Form
CRS	Clinical Research Site
DAIDS	Division of Acquired Immunodeficiency Syndrome
EFV	Efavirenz
FBC	Full blood count
FTC	Emtricitabine
GCP	Good Clinical Practice
HIV	Human Immunodeficiency Virus
HBV	Hepatitis B Virus
ITT	Intention to treat
LFT	Liver function test
LPV/r	Lopinavir/Ritonovir
NRTI	Nucleotide Reverse Transcriptase Inhibitor
PEPFAR	Presidents Emergency Plan For AIDS Relief
PHC	Primary health care
PrEP	Pre-Exposure Prophylaxis
PID	Participant identification
QA	Quality assurance
SAE	serious adverse event
SAP	Statistical Analysis Plan
SOP	Standard Operating Procedures
STI	Sexually transmitted infection
TDF	Tenofovir disoproxil fumarate
WHO	World Health Organisation

## Open Label Randomized Controlled Trial to Assess the Impact of prophylactic exposure to tenofovir gel on the efficacy of subsequent tenofovir-containing antiretroviral therapy on viral suppression

### STUDY SCHEMA

Purpose:	To determine whether prophylactic exposure to tenofovir gel alters the therapeutic response to a tenofovir containing antiretroviral regimen				
Study design:	Open label, two-arm, randomised controlled trial				
Study population:	Women who become infected with HIV while participating in the CAPRISA 004 and CAPRISA 008 trials. There are 3 study populations: Study population 1: HIV positive women from the CAPRISA 004 tenofovir gel arm and HIV positive women from the clinical trial tenofovir gel provision arm of CAPRISA 008 Study population 2: HIV positive women in the placebo arm of CAPRISA 004 Study population 3: HIV positive women from the family planning service arm of CAPRISA 008				
Study sites:	CAPRISA eThekweni and CAPRISA Vulindlela clinics.				
Study duration:	3 years				
Study intervention:	Enrolled women will be initiated on their assigned antiretroviral therapy regimen when they reach any of the following criteria: 

• reach a CD4+ count of less than 350 cell/mm^3

• acquire an AIDS defining illness

• become pregnant - women in any of the three study populations who become pregnant during follow-up will be initiated on their assigned treatment regimen, as appropriate, for prevention of mother-to-child transmission of HIV.

 
At enrolment women in each of the three study populations will be assigned randomly to one of the two following antiretroviral regimens
 

Intervention Arm:	Tenofovir, lamivudine and efavirenz	

Control arm:	Zidovudine, lamivudine and efavirenz	

	Intervention Arm:	Tenofovir, lamivudine and efavirenz	Control arm:	Zidovudine, lamivudine and efavirenz
Intervention Arm:	Tenofovir, lamivudine and efavirenz				
Control arm:	Zidovudine, lamivudine and efavirenz				
Sample size:	The projected sample size is 90 women. The number of women in each stratum is as follows: Study population 1: n = 40 Study population 2: n = 30 Study population 3: n = 20				
Primary endpoint:	The primary endpoint is the antiretroviral treatment failure rate at 12 months. Treatment failure is defined as viral load > 50 copies/ml, antiretroviral regimen changes for treatment failure or death				
Secondary Endpoints:	

1. Change in CD4+ cell count from the earliest post-infection timepoint to the time of randomisation to 12, 24 and 36 months post-randomisation

2. Tenofovir resistance, defined as presence of K65R, K70E or any of the TAMS mutations.

3. Reported adverse events with severity grades 3 and 4 based on the DAIDS toxicity grading tables

4. Cellular and humoral immune responses

5. Genital viral shedding (viral load on tear flow)

				
Ancillary Endpoint	Mother-to-child HIV transmission rates as determined by PCR on infant at 6 weeks.				

# Open Label Randomized Controlled Trial to Assess the Impact of prophylactic exposure to tenofovir gel on the efficacy of subsequent tenofovir-containing antiretroviral therapy on viral suppression

## 1. Background and Rationale:

The HIV/AIDS pandemic remains among our greatest public health challenges. The overall number of people living with HIV is increasing as new infections continue to occur and AIDS deaths are prevented by increasingly available antiretroviral therapy (ART). Globally, there were an estimated 33.2 million people living with HIV infection or AIDS and annual incidence of new HIV infections was an estimated 2.7 million in 2007 [1] emphasizing the urgent need for safe and effective methods of HIV prevention especially in Africa, a region which accounts for 70% of the global burden of disease[1]. In the absence of an effective vaccine, focus has shifted to other prevention strategies such as pre-exposure prophylaxis.

Tenofovir, an adenosine nucleotide analog with potent activity against retroviruses[2], was initially developed and tested as a prophylactic in monkeys and was subsequently formulated for oral use as tenofovir disoproxil fumarate (Viread®), which is now widely used for HIV treatment. The efficacy of Viread® has been demonstrated in treatment-experienced and naïve patients.[3, 4] In antiretroviral-naïve patients, the combination of tenofovir with lamivudine and efavirenz has been classified as a preferred regimen in the Department of Health and Human Services treatment guidelines[5], and has been adopted by the South African Department of health as the first line regimen in treatment-naïve HIV infected patients since April 2010. The durability of antiviral response, favourable resistance profile, once daily dosing, and excellent long term safety profile of tenofovir [6], makes this drug an attractive option in both treatment and prevention regimens and its long half-life [7], made it an ideal choice as the first antiretroviral drug to be formulated as a microbicide gel.

Tenofovir has been used in the majority of prevention studies testing the concept of Pre-exposure Prophylaxis (PrEP) as a prevention strategy to date. Currently there are five large- scale trials assessing oral pre-exposure prophylaxis with tenofovir or tenofovir-emtricitabine.[8] The results of the CAPRISA 004 study conducted in South Africa released in July 2010 which tested the effectiveness and safety of 1% tenofovir gel showed that the use of tenofovir in a gel formulation reduced HIV acquisition by 39% overall, and by 54% in women with high gel adherence.[9] The Microbicides Trial Network (MTN 003 trial) is assessing the effectiveness of daily tenofovir gel, tenofovir oral or tenofovir-emtricitabine oral tablets.[10]

There have been concerns raised regarding the use of tenofovir in both PrEP and treatment regimens due to the potential for selection of viral mutations and development of resistance in patients who have become HIV-infected while on PrEP.

Previous experience with the use of antiretroviral drugs in both prevention and treatment of HIV comes largely from the use of nevirapine (NVP) in prevention of mother to child transmission (PMTCT) programs, especially in resource limited settings. Prophylactic use of NVP readily selects viral mutations that promote resistance to non nucleoside reverse-transcriptase inhibitors (NNRTIs)[11-14] that are recommended as part of first line adult treatment regimens.[15] NVP added to short-course zidovudine treatment resulted in reduced viral suppression 6 months after the commencement of therapy in a randomized trial from Thailand.[16] A subsequent study from seven African countries found that treatment with a NVP-sparing regimen was superior to a regimen containing NVP in women with prior exposure peripartum single-dose NVP.[17] The superiority of the NVP-sparing regimen was present both in women who had and did not have detectable resistance to NVP [17]. A study from Zambia reported that sdNVP exposure occurring 16 months before therapy was initiated had no impact on clinical outcomes or CD4 cell count.[18] The proportion of women who have detectable viral drug-resistance mutations decreases after exposure to NVP, providing a rationale for these findings.[14, 19, 20] A study conducted in Johannesburg found that exposure to single dose nevirapine in the prior 18-36 months was not associated with a reduced likelihood of achieving and sustaining viral suppression while receiving NNRTI based therapy. [21]

There have been no studies conducted to determine whether the use of tenofovir in pre-exposure prophylaxis affects treatment outcomes in patients who subsequently use tenofovir, which is part of the first line antiretroviral therapy regimen of many countries including South Africa. Resistance to tenofovir is associated with the K65R mutation in the reverse transcriptase gene. A separate pattern of tenofovir resistance is conferred by 3 or more thymidine analogue resistance mutations (TAMS), particularly M41L or L210W. The T69S insertion mutations, associated with resistance to multiple nucleoside analogues is also associated with resistance to tenofovir. An *in vitro* study suggested that subtype C viruses have a higher propensity to develop the K65R mutation compared to subtype B viruses, when cultured in the presence of TFV alone [22] but these findings remain controversial. It is not known if the development of viral resistance mutations in persons on PrEP may lead to less fit viruses, which may be rapidly replaced by wild virus, and therefore the future ARV treatment options are difficult to predict.

In a PrEP trial conducted in Ghana, no tenofovir-related resistance mutations were found in one seroconverter in the tenofovir arm.[23] In a Phase II trial of 1% tenofovir gel (HPTN 050), no new resistance mutations were detected in plasma and cervicovaginal lavage after 14 days of product use in HIV-infected women.[24]. Similarly, no tenofovir-related resistance mutations were found in the CAPRISA 004 tenofovir gel trial.[9]

This study aims to determine whether prophylactic exposure to tenofovir gel alters the therapeutic response to a tenofovir containing antiretroviral regimen

## **2. Study Objectives**

### **2.1 Primary Objective:**

To determine whether prophylactic exposure to tenofovir gel at the time of infection alters the subsequent therapeutic response to a tenofovir containing antiretroviral regimen

### **2.2 Secondary Objectives:**

1. To assess whether prophylactic exposure to tenofovir gel at the time of infection alters the rate of CD4+ cell count decline (HIV disease progression) and subsequent rebound following initiation of tenofovir containing or tenofovir-sparing antiretroviral treatment
2. To assess the role, if any, of tenofovir resistance on the therapeutic response to tenofovir containing antiretroviral treatment
3. To assess the safety of tenofovir containing antiretroviral treatment in women exposed to tenofovir gel at the time of HIV acquisition
4. To assess whether exposure to tenofovir gel at the time of HIV acquisition alters the subsequent humoral and cellular immune responses following antiretroviral treatment initiation
5. To assess whether prophylactic exposure to tenofovir gel at the time of HIV acquisition influences genital viral shedding and the prevalence of tenofovir resistance in genital tract viruses

### **2.3 Ancillary objective**

To assess whether tenofovir containing antiretroviral treatment regimen following prophylactic exposure to tenofovir gel at the time of HIV acquisition, is effective in preventing HIV transmission in pregnancy

### **2.4 Primary endpoint:**

The primary endpoint is the antiretroviral treatment failure rate at 12 months. Treatment failure is defined as viral load > 50 copies/ml, antiretroviral regimen changes for treatment failure or death

## 2.6 Ancillary Endpoint

Mother-to-child HIV transmission rates as determined by PCR on the infant at 6 weeks.

## 3. Methods

### 3.1 Study Overview

This study is an open label, two-arm, randomised control trial comparing treatment outcomes in women previously exposed to tenofovir gel at the time of HIV acquisition, who are randomised to either a tenofovir containing or a tenofovir-sparing antiretroviral treatment regimen. Comparisons in treatment outcomes will also be made between tenofovir gel exposed and tenofovir gel unexposed women following tenofovir containing antiretroviral treatment initiation. Approximately 90 women who have seroconverted while in the active or placebo arms of the CAPRISA 004 (Phase IIb Trial to Assess the Safety and Effectiveness of the Vaginal Microbicide 1% tenofovir Gel for the Prevention of HIV Infection in Women in South Africa) study and the CAPRISA 008 (Phase IIIb Open-Label Randomized Controlled Trial to Assess the Effectiveness and Safety of Tenofovir Gel Provision through Family Planning Services in KwaZulu-Natal, South Africa) study will be enrolled. Enrolment into the study will coincide with eligibility for ART initiation. Following enrolment, at which the assigned ART regimen is initiated, women will be followed up at week 1, month 1, 3, 6, 12, 18, 24, 30 and 36. The primary endpoint is the antiretroviral treatment failure rate at 12 months. Treatment failure is defined as viral load > 50 copies/ml, antiretroviral regimen changes for treatment failure or death. In addition CD4+ monitoring, viral resistance testing, adverse event reporting and blood and mucosal immunology assays will be conducted to fulfil the secondary objectives of the study. The anticipated total study duration is approximately 36 months of follow-up after ART initiation.

### 4. Study setting:

CAPRISA eThekweni Clinical Research site, Durban, South Africa:

CAPRISA eThekweni CRS is located adjacent to the Prince Cyril Zulu Communicable Disease Centre (CDC), a designated PHC of the Durban City Health Department, for the diagnosis and treatment of STIs and tuberculosis.

CAPRISA Vulindlela Clinical Research Site, KwaZulu-Natal, South Africa:

The Vulindlela CRS is situated in the sub-district of Vulindlela, a rural community, with approximately 250,000 residents in the KwaZulu-Natal midlands, about 150 km north-west of Durban.

### 5. Study Population:

Women who become infected with HIV while participating in the CAPRISA 004 and CAPRISA 008 trials.

There are 3 study populations:

- Study population 1:* HIV positive women from the CAPRISA 004 tenofovir gel arm and HIV positive women from the clinical trial tenofovir gel provision arm of CAPRISA 008
- Study population 2:* HIV positive women in the placebo arm of CAPRISA 004
- Study population 3:* HIV positive women from the family planning service arm of CAPRISA 008

Women in any of the three study populations who become pregnant during follow-up will be initiated on their assigned treatment regimen, as appropriate, for prevention of mother-to-child transmission of HIV.

#### 5.1 Inclusion Criteria:

1. Age 18 years or older
2. Previously enrolled in the CAPRISA 004 or CAPRISA 008 study – placebo or active arms
3. Able and willing to provide informed consent to be screened for, and to enrol in, the study
4. Able and willing to provide adequate locator information for study retention purposes
5. Confirmed HIV infection in the CAPRISA 004 or 008 trial
6. Agree to adhere to study visits and procedures

#### 5.2 Exclusion criteria:

1. Currently on antiretroviral therapy (including PMTCT prophylaxis)

2. Has any other condition that, based on the opinion of the Investigator or designee, would preclude provision of informed consent, make participation in the study unsafe, complicate interpretation of study outcome data, or otherwise interfere with achieving the study objectives.

### **5.3 Recruitment:**

Participants who have seroconverted while enrolled in the CAPRISA 004 study or the CAPRISA 008 study will be recruited for study participation. Participants who acquired HIV infection while in follow-up in the CAPRISA 004 study are currently in follow up in the CAPRISA 002 study (Viral Set Point and Clinical Disease Progression in HIV-1 subtype C infection: the role of immunological genetic and viral factors over the course of disease and during antiretroviral therapy, acute and early infection). All participants who become infected with HIV while in the CAPRISA 008 study will be referred to the CAPRISA 002 study for follow-up. When participants in CAPRISA 002 become eligible for antiretroviral therapy, they will be referred to this study for screening and enrolment.

### **5.4 Screening, Enrolment and Randomisation:**

Study participants will be screened for eligibility and participants meeting eligibility criteria will be enrolled in the study. Eligibility will be confirmed prior to enrolment. PID assignment will be done at enrolment. Enrolment into the study will coincide with ART initiation. Randomisation to either the intervention or control arm will be done at enrolment/ART initiation in a 1:1 ratio (see section 9.2).

### **5.5 Follow up:**

Follow up visits will follow the study schedule of evaluations (Appendix 1). Participants will be followed up for a maximum period of 36 months post antiretroviral treatment initiation following which participants will be transitioned into CAPRISA 002 phase V or the CAPRISA AIDS treatment (CAT) programme where antiretroviral treatment and clinical care will continue.

### **5.6 Retention:**

The CAPRISA DataFax system will serve as an electronic tracking system to allow study staff to monitor and track participants who have missed scheduled study visits. Participants will be contacted telephonically to follow up missed visits. If unable to contact participant telephonically a tracking team will conduct home visits and assist participants who require transport to clinic.

### **5.7 Participant Withdrawal**

Participants may voluntarily withdraw from the study for any reason at any time. Participants may be withdrawn from the study by designated staff in order to protect their safety and/or if they are unwilling or unable to comply with required study procedures following consultation with the PIs. Participants may also be withdrawn if the study is terminated prior to its planned end date.

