## 9. Statistical Considerations

### 9.1 Sample Size:

The total number of women with HIV infection in the CAPRISA 004 and CAPRISA 008 studies is anticipated to be approximately 120 in the tenofovir gel exposed group. In addition 60 participants seroconverted in the 004 study on the placebo treatment arm.

If 50% of these participants need to be initiated on ART within the next 3 years, we would be able to randomise approximately 60 participants who were exposed to tenofovir gel to ART assignment. We also anticipate that 30 participants who seroconverted on the placebo arm will be eligible for randomisation to treatment assignment in the next 3 years (Table 1).

There are 3 study populations:

*Study population 1:* HIV positive women from the CAPRISA 004 tenofovir gel arm and HIV positive women from the clinical trial tenofovir gel provision arm of CAPRISA 008

*Study population 2:* HIV positive women in the placebo arm of CAPRISA 004

*Study population 3:* HIV positive women from the family planning service arm of CAPRISA 008

Participants will be randomised in each of the tenofovir gel exposed groups and the placebo gel exposed groups to either a tenofovir containing antiretroviral regimen or a tenofovir-sparing antiretroviral regimen.

The primary treatment outcome, treatment failure (treatment failure includes viral load > 50 copies/mL at 12 months, regimen changes for treatment failure within the first 12 months or death within the first 12 months), will be analysed in four different comparisons.

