**9.3 Data analysis plan**

A Statistical Analysis Plan (SAP) will outline the statistical analyses. The following is a summary of the planned analyses. Any deviations to be made from this summary plan will be documented in the detailed SAP.

A Fisher's exact test will be used to compare the proportion of participants with treatment failure in each of the two arms. We will also do a stratified Mantel Haenszel test where the stratum is the study arm a participant who seroconverted while randomised to tenofovir was in (004, 008 CAPRISA arm or 008 family planning arm). Placebo arm patients will not be stratified.

In addition, treatment failure at 24 and 36 months will be compared between the treatment arms using the same statistical methods as for the primary comparison at 12 months.

All primary analyses will be performed on an intention-to-treat (ITT) basis with additional analyses performed on the per protocol and as treated populations. For the ITT analysis, participants will be analysed according to the study arm, even if the participant did not follow the assigned procedures. The only participants excluded from this primary analysis population will be women with no post-randomisation visit and no data collected. All primary and secondary analyses will be two-sided and will be performed at the 0.05 level of significance.

The analyses of secondary objectives will be described in detail in the SAP.

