## Appendix 1: Schedule of evaluations

	V0	V1	V2	V3	V4	V5	V6	V7	V8	V9	V10
	Scr	Enr	W1	M1	M 3	M 6	M12	M18	M24	M30	M36
CONSENT/ADMIN											
Informed Consent	X	X									
Storage consent		X									
Locator Info	X	X	X	X	X	X	X	X	X	X	X
Risk Reduction		X	X	X	X	X	X	X	X	X	X
Eligibility assessment	X	X									
Randomisation		X									
Adherence support counselling	X	X									
CLINICAL											
Pregnancy test	X	X	X	X	X	X	X	X	X	X	X
FBC	X	X				X	X	X	X	X	X
U+E and Creatinine	X	X				X	X	X	X	X	X
Cholesterol, Trig		X					X		X		X
LFT		X					X		X		X
Fe/B12/Fol		X					X		X		X
Ca/Mg/PO4		X					X		X		X
STI											
RPR		X					X		X		X
HSV & HBV		X					X		X		X
BV		X					X		X		X
GC/CT-VVS		X					X		X		X
VIROLOGY											
RT-PCR/VL		X	X	X	X	X	X	X	X	X	X
Viral isolation		X	X	X	X	X	X	X	X	X	X
Seq (RNA/DNA)		X	X	X	X	X	X	X	X	X	X
Seq mucosal (CVL)		X					X		X		X
IMMUNITY ASSAYS											
	X	X	X	X	X	X	X	X	X	X	X
STORAGE											
Storage-Serum		X	X	X	X	X	X	X	X	X	X
Storage-PBMC		X	X	X	X	X	X	X	X	X	X
MUCOSAL IMMUNOLOGY											
Tear Flo Strips		X					X		X		X
Cytobrush		X					X		X		X
RESISTANCE TESTING											
ARV resistance plasma		X	X	X	X	X	X	X	X	X	X
Tenofovir resistance: Cytobrush		X					X		X		X
Approximate Blood Draw Volumes	13ml	117ml	95ml	95ml	103ml	112ml	117ml	112ml	117ml	112ml	117ml

Note:

1. Enrolment coincides with day of ART initiation
2. These are the study visits. In addition participants will be seen every month for the first 6 months following ART initiation
3. Any test may be performed when clinically indicated

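### Staff who know the arm may withdraw a woman from the whole study for not complying with study procedures, and nothing provides for collecting her month-12 outcome afterwards

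*Protocol*

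**What the plan says.** Section 5.7 lets a woman leave at her own wish, and lets staff remove her: "Participants may be withdrawn from the study by designated staff in order to protect their safety and/or if they are unwilling or unable to comply". The sentence then names what has to be complied with and adds one safeguard, namely "with required study procedures following consultation with the PIs". What she is withdrawn from is the study. The section does not separate stopping one procedure, stopping the assigned regimen and ending follow-up.

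Section 9.3 defines the primary analysis as intention-to-treat: "participants will be analysed according to the study arm, even if the participant did not follow the assigned procedures". It allows one exclusion: "The only participants excluded from this primary analysis population will be women with no post-randomisation visit and no data collected".

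Section 9.1 gives the primary outcome: "treatment failure includes viral load > 50 copies/mL at 12 months, regimen changes for treatment failure within the first 12 months or death within the" – and here the sentence sets the same 12-month limit for deaths. Section 9.3 repeats the comparison at 24 and 36 months.

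Two sections bear on what happens to absent women. Under section 5.6, "Participants will be contacted telephonically to follow up missed visits", with home visits if that fails; this covers missed visits, not women already withdrawn. Under section 5.5, after at most 36 months on treatment, "participants will be transitioned into CAPRISA 002 phase V or the CAPRISA AIDS treatment (CAT) programme where antiretroviral treatment and clinical care will continue".

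Section 9.2 says that the trial is open label once the envelope is opened. In Appendix 1 the row "Approximate Blood Draw Volumes" shows 95 to 117 ml at every visit from enrolment on, and mucosal sampling is scheduled at enrolment and months 12, 24 and 36.

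**The concern.** The same behaviour is treated in two ways. Section 9.3 says that failing to follow procedures does not take a woman out of the analysis. Section 5.7 makes it a ground for ending her participation, and with it the collection of the data that the analysis needs. A SAP can decide how to score a missing viral load, but it cannot recover one that was never collected.

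The loss need not be neutral. The procedures are demanding, and difficulty in keeping to them could plausibly go with poor adherence to treatment and so with viral load. Safety withdrawals could differ between regimens. The decision is discretionary, has no written criteria beyond consultation with the principal investigators, and is made with the arm known. With about 30 women per arm in the largest comparison, a handful of such losses can matter. The 24- and 36-month comparisons are exposed for longer.

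**Working it through.** **Inputs.** From section 9.1: 30 women per arm in Comparison A; proportions 0.9 vs 0.6, that is, failure 0.10 vs 0.40; Fisher's exact test, two-sided 0.05; stated power 70%. The protocol gives no withdrawal rate and no link between withdrawal and failure. Every loss figure below is therefore an assumption.

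**The plan's own figures.** Summing the two binomial probabilities over all tables that Fisher's test rejects (each tail at most 0.025) gives 70.5% for Comparison A (stated 70%), 25.4% for B (stated 25%) and 43.5% for C and D (stated 43%). All three reproduce.

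**Illustration with counts.** The expected failures are 0.40 × 30 = 12 and 0.10 × 30 = 3. Suppose that withdrawals fall only among the 12 failures.

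| Situation | High-failure arm | Other arm | Difference | Two-sided p |
|---|---|---|---|---|
| All outcomes kept | 12/30 = 0.400 | 3/30 | 0.300 | 0.015 |
| Two failures lost | 10/28 = 0.357 | 3/30 | 0.257 | 0.027 |
| Three failures lost | 9/27 = 0.333 | 3/30 | 0.233 | 0.0498 |
| Four failures lost | 8/26 = 0.308 | 3/30 | 0.208 | 0.090 |
| Two failures kept and counted as successes | 10/30 = 0.333 | 3/30 | 0.233 | 0.057 |

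A lost outcome leaves both numerator and denominator. On that reading, two losses do not cross 0.05, three sit on the boundary and four cross it. Two are enough only if withdrawn women are counted as successes, which no section proposes.

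**Illustration with power.** Let a fraction *f* of failures and a fraction *g* of non-failures be lost. The failure proportion then seen in an arm with true proportion *p* is

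p(1−f) / [p(1−f) + (1−p)(1−g)].

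- f = 0.25, g = 0.05 in both arms: 0.30/(0.30 + 0.57) = 0.345 and 0.075/(0.075 + 0.855) = 0.081. The difference is 0.264 and about 26 and 28 women remain. Power is 57%.
- f = 0.50, g = 0.05 in both arms: 0.20/(0.20 + 0.57) = 0.260 and 0.05/(0.05 + 0.855) = 0.055. The difference is 0.204 (before rounding) and about 23 and 27 women remain. Power is 37%.
- f = 0.50, g = 0.05 in the high-failure arm only: 0.260 vs 0.100, with 23 and 30 women. Power is about 20%.
- Loss unrelated to outcome, 10% or 20%: the difference stays at 0.30. Power is 63% or 60%.

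Neutral loss costs some power and leaves the difference alone. Loss concentrated among failures shrinks the difference itself.

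**The case against.** The strongest reply is that section 5.7 is permissive, requires consultation with the principal investigators, and speaks of study procedures, not of adherence to treatment or virological failure. The protocol also handles most trouble inside the study. Section 8.1 offers adherence counselling when compliance looks low. Section 7.1 provides for drug switches and second-line treatment. Section 5.6 traces missed visits. A regimen change for failure within 12 months, or a death, counts as an event without a month-12 viral load. Viral load is also scheduled at week 1 and months 1, 3 and 6, so a woman withdrawn late leaves earlier values. All of this stands, and it makes the number of affected women likely to be small.

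It also rules out some stronger readings that a reader might infer:

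- That outcomes are in fact lost selectively in the women most likely to fail. The documents give no withdrawal rate and no such link.
- That the intention-to-treat set is breached. A withdrawn woman with a post-randomisation visit or any data stays in it under her assigned arm; what may be missing is her outcome.
- That two staff decisions among 60 women change the verdict either way. Two lost failures leave p=0.027. Moving from 10 to 12 failures (p=0.057 to 0.015) needs withdrawn women scored as failures when they were in fact suppressed. Both flips turn on scoring, which the SAP may settle.
- That the outcome is recoverable from CAPRISA 002 or CAT. Section 5.5 describes that transfer after the 36-month maximum and does not say that a woman withdrawn early enters either programme.

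The reply does not answer the central point: no section provides for collecting the outcome once staff have withdrawn a woman.

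**Conclusion.** The point holds as a cheap improvement. Section 5.7 permits withdrawal from the whole study for non-compliance with procedures, by staff who know the arm, without continued outcome collection. That creates a risk of outcome-related loss at months 12, 24 and 36 and undercuts the analysis that section 9.3 intends, without formally contradicting it.

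The size is conditional on assumed losses. Starting from 12 vs 3 failures among 30 vs 30, losing two of the 12 moves p from 0.015 to 0.027, and losing four moves it to 0.090. With 25% to 50% of failures and 5% of non-failures lost in both arms, the difference falls from 0.30 to between 0.264 and 0.204, and power from 70.5% to between 57% and 37%. If few women are withdrawn, or withdrawal is unrelated to outcome, the effect is smaller. How missing values are scored is left to the SAP and is not part of this point.

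**What to change.** Amend section 5.7 in two ways.

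1. Non-compliance with a study procedure ends that procedure only, not follow-up.
2. For any woman who is withdrawn by staff or stops her assigned regimen, continue, with her consent, to collect the viral load nearest months 12, 24 and 36, vital status and current regimen. Do this at study visits, or from CAPRISA 002 or CAT records where she is in care there. Add a sentence on this to the consent form.

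Decisions to stop treatment or procedures for safety stay with the clinicians. This change concerns data collection only and does not alter the safety ground in section 5.7.

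The cost is a protocol amendment, a consent sentence and some record abstraction. The downside is that routine values may fall outside the visit window.
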